4.4. Assessment Schedule and Procedures

Potential participants will complete screening to determine eligibility prior to enrollment. Interested and eligible participants will be scheduled for an assessment visit. At the beginning of Visit 1, participants will be provided the Whoa Baby Phase 2 informed consent and HIPAA authorization for review and completion. After signing the Whoa Baby Phase 2 informed consent and HIPAA authorization, participants will complete several procedures at the Visit 1. See **Table 3**, Phase 2 Schedule of Procedures.

TABLE 3. Phase 2 Schedule of Procedures

Visit Assessment	Visit 1
Informed Consent (Adult)	X
Height	X
Weight	X
Individual Interview	X
Infant Formula Preparation	X

4.4.1. Visit 1

When an individual arrives to Visit 1 at the PBRC Demonstration Kitchen, the Whoa Baby Phase 2 informed consent will be provided for reading and review. If the participant agrees, the participant will sign the consent prior to the initiation of study procedures. After signing the informed consent, participants will learn of their group assignment and study procedures will be completed as part of Visit 1. Height and non-fasting body weight will be measured by trained study staff. Individuals will be asked to participate in an individual interview and prepare servings of powdered infant formula following the instructions provided.

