4.5.2. Individual Interview

Study staff will give participants a brief structured interview to collect general information, e.g. age, race, income, education, typical use of infant formula, number of children and caregiver status.

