4.5.3. Infant Formula Preparation

Participants will be asked to prepare 2 trials of 2, 4, 6, and 8 fl oz bottles of infant formula in random order. A total of 8 formula bottles will be prepared at Visit 1. For each bottle, the participant will follow their randomly assigned (Group 1 or Group 2 randomization) preparation instructions to measure the required amount of powdered formula. The participant will dispense the respective number of scoops of powdered formula into the formula bottle depending on which size bottle is being prepared. After all powdered formula is dispensed into the feeding bottle, PBRC staff will weigh the formula bottle with powdered formula only. The participant will continue following the instructions and pour water into the bottle and mix the formula. PBRC staff will weigh the formula bottle. This procedure will be repeated to assess intra- individual variability. Bottles will be weighed (to the nearest tenth of a gram) using a METTLER TOLEDO PB3001 scale, and dry formula and prepared formula weights will be recorded. Study staff who record the formula weights will be blinded to the randomization assignment and intended bottle size.

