6.2. Whoa Baby Phase 2 Randomization

A total of 150 participants will be randomized to one of two groups in Phase 2. A randomization schedule will be created and the study coordinator will ensure that each enrollee is put into the correct group. In addition to participant randomization, bottle size preparation order will also be randomized. At the visit, participants will receive a slip of paper revealing the order in which to prepare each bottle. A biostatistician will create the randomized sequences and each participant will be asked to prepare the bottles as dictated by the sequence provided to them.

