6.3. Data Analysis Plan

To address the primary aim, dry formula weights will be compared to package recommendations (i.e. 8.7 g per scoop) and classified as under-scooped, accurate scoop, or over-scooped. The proportion of bottles that are over-scooped will be compared between the two groups. Both univariate and multivariate analyses will be employed. 2x2 contingency tables with counts of participants over-scooping in each treatment arm will be constructed and chi-square tests used to compare raw proportions. This will be carried out separately for each bottle size. In addition, estimated probabilities of over-scooping for each group will be obtained from logistic regression models allowing for adjustments for bottle size and any other chosen covariates. Group-level odds ratios constructed from the estimated probabilities will be compared using two-sample t-tests. For all tests, statistical significance is defined as $p < \alpha$. Adjustments for multiple comparisons will be made when appropriate.

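### Participants learn their arm before the interview and the scooping, so an expectation effect could mix with the effect of the instructions; later, neutral disclosure would reduce this at little cost

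*Combined protocol and SAP*

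**What the plan says.** All references are to the combined protocol and SAP.

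- **Section 4.4.1 (Visit 1)** sets the order of the visit. Once consent is signed, "participants will learn of their group assignment and study procedures will be completed as part of Visit 1". Height and weight come next in the text, and then: "Individuals will be asked to participate in an individual interview and prepare servings of powdered infant formula following the instructions provided".
- **Section 4.5.2** lists what the interview collects: "age, race, income, education, typical use of infant formula, number of children and caregiver status".
- **Section 4.5.3** has the participant scoop the powder for eight bottles, and staff weigh each bottle. It contains the only blinding statement for Phase 2: "Study staff who record the formula weights will be blinded to the randomization assignment", and also to the intended bottle size.
- **Section 6.2** adds that "participants will receive a slip of paper revealing the order in which to prepare each bottle", from sequences that a biostatistician draws up.
- **Section 6.3** plans chi-square tests of over-scooping by arm, and logistic models "allowing for adjustments for bottle size and any other chosen covariates".

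No section states whether participants or interviewers are blinded, whether the instruction sheets carry a group label, or how the two groups are described to participants. The consent pages are not part of the reviewed text, so their wording cannot be judged.

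**The concern.** The scale reading is objective, but what is put on the scale is not independent of the participant. Levelling a scoop takes care, and care can change with what a person believes about the task. Aim 2 credits any gain to easier reading and explicit pictures. If participants also know which arm they are in, the arms may differ in a second respect that has nothing to do with the content of the sheet, and the between-arm comparison cannot separate the two. A larger sample does not help, because this would be a bias and not noise.

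Following the instructions requires having the sheet. It does not require knowing which arm the sheet stands for. The disclosure is therefore largely avoidable.

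Two lesser exposures follow from the same ordering. Interview answers are collected after disclosure and could enter the adjusted models. An informed participant could also mention the arm to the staff who weigh the bottles.

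**Working it through.** **Inputs**

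- 75 participants per group (section 6.1).
- Over-scooping with the existing instructions: 0.80 (Table 4). Aim 2 uses 89%.
- Over-scooping hoped for with the new instructions: 0.50 (section 6.1 and Aim 2).
- Significance level: section 6.3 gives no value, so two-sided 0.05 is assumed.
- Size of an expectation effect: not in the documents. Drops of 2, 5, 10 and 15 points are assumed to show a range.

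**Step 1: reproduce Table 4.** With p̄ = (p₁ + p₂)/2,

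n = [1.96 √(2p̄(1−p̄)) + 0.842 √(p₁(1−p₁) + p₂(1−p₂))]² / (p₁ − p₂)²

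For 0.80 against 0.50: [1.96 × 0.6745 + 0.842 × 0.6403]² / 0.09 = 1.861² / 0.09 = 38.5, rounded up to 39. The other rows come out at 294, 82 and 23. All four match the table. The two-sided version with continuity correction (313, 91, 45, 28) does not match, nor does the one-sided version without it (231, 64, 31, 18). This supports the two-sided 0.05 assumption.

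**Step 2: rejection rate if the instructions do nothing.** Let p₁ = 0.80 in Group 1 and p₂ = 0.80 − b in Group 2, where b is due to expectation alone. With n = 75,

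SE₀ = √(2p̄(1−p̄)/n), SE₁ = √([p₁(1−p₁) + p₂(1−p₂)]/n)

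P(reject) = Φ((b − 1.96 SE₀)/SE₁) + Φ((−b − 1.96 SE₀)/SE₁)

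| b | p₂ | SE₀ | SE₁ | P(reject) |
|---|---|---|---|---|
| 0.05 | 0.75 | 0.0682 | 0.0681 | 11.3% |
| 0.10 | 0.70 | 0.0707 | 0.0702 | 29.2% |
| 0.15 | 0.65 | 0.0729 | 0.0719 | 53.9% |

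For b = 0.05: (0.05 − 0.1337)/0.0681 = −1.23, so Φ = 0.110; the far tail adds about 0.003. A drop of only 2 points gives 6.0%. Starting from the 0.89 of Aim 2, drops of 2, 5, 10 and 15 points give 6.6%, 14.5%, 38.5% and 66.0%.

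**Step 3: scale of the assumed drops.** Against the 30-point gap in Table 4, 5, 10 and 15 points are 17%, 33% and 50%. Against the 39-point gap in Aim 2 (89% to 50%), they are 13%, 26% and 38%.

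**Step 4: room in the design.** At 75 per group, power for 0.80 against 0.50 is 97.7%. If 5 or 10 of the hoped-for 30 points were expectation and vanished, power for the remainder (0.80 against 0.55 or 0.60) would be 91.3% or 76.7%.

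**The case against.** The strongest reply is that the mechanism goes beyond the text. The plan says that participants learn their group. It does not say that they are told theirs is the new or better version, or which result is expected. The arms are called Group 1 and Group 2, and the consent wording, which is not available, may already be neutral. This stands. A reader might infer that participants are told they hold improved instructions, and the documents do not support that. What remains is that the plan discloses the assignment early and states no limit on how the groups are described.

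Second, full blinding is impossible. Participants must read their sheet, and plain language, pictures and layout are the intervention. Some controls may recognise the package text. Reordering alone does nothing for the scooping, since the sheet is seen before the first bottle in any case. This also stands, and it limits what the fix can claim.

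Third, the direction is not established. Both arms know that their bottles are weighed, so some extra care is shared. In the preliminary study 95% of bottles were overfilled and caregivers did no better than non-caregivers. The authors read this as a failure to understand the label, which points to comprehension more than effort. That weakens any claim that disclosure must favour the new instructions, but it does not rule out an expectation effect.

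Fourth, the two lesser exposures are small. Age, race, income, education and number of children will hardly shift with knowledge of the arm; typical formula use and caregiver status might. No interview item is committed to a model, and the chi-square tests use no covariates. Weights read to a tenth of a gram leave recorders little latitude.

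**Conclusion.** The point holds as a low-cost improvement to a stated procedure. Participants learn their arm before the interview and the scooping, the outcome depends partly on their care, and blinding is stated only for the weight recorders. An expectation effect could therefore be mixed into the estimate of what the wording and pictures achieve.

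Its size and direction are unknown. The figures of about 11%, 29% and 54% are correct arithmetic on assumed drops of 5, 10 and 15 points from 0.80, with no true instruction effect, 75 per arm and two-sided 0.05. They show how sensitive the comparison is to such drops. They are not evidence that a bias of that size exists.

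Two stronger readings should be avoided. A reader might conclude that the present order biases the trial toward a positive result, but nothing in the documents fixes the sign. A reader might also conclude that unlabelled sheets would remove the problem, but the versions differ visibly, so the effect can only be reduced. Protection of the interview answers, mainly typical formula use and caregiver status, is a secondary benefit.

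**What to change.** - In section 4.4.1, set the order as consent, height and weight, interview, and only then the assigned instructions.
- Hand the instructions over in one packet with the bottle-order slip of section 6.2, to be opened after the interview. Put no group label on the sheet.
- In the consent and at the visit, describe the sheet only as one of two versions. As far as the IRB allows, do not say which is new or which is expected to do better.
- Leave the layout and pictures of each version intact, because they are what is being tested.
- Ask participants not to mention their version to the weighing staff.
- State in the protocol who is blinded and who is not: participants, interviewers and weight recorders.

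The cost is a changed visit order, neutral consent wording with whatever IRB review that needs, and packet preparation. No extra visits or participants are needed, and the sample size does not change.

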4.5. Measures and Outcome Assessments

4.5.1. Anthropometrics

Height and body weight will be measured using standard procedures of PBRC. Non-fasting body weight will be recorded. Body mass index (BMI) will then be calculated from the recorded height and body weight.

4.5.2. Individual Interview

Study staff will give participants a brief structured interview to collect general information, e.g. age, race, income, education, typical use of infant formula, number of children and caregiver status.

4.5.3. Infant Formula Preparation

Participants will be asked to prepare 2 trials of 2, 4, 6, and 8 fl oz bottles of infant formula in random order. A total of 8 formula bottles will be prepared at Visit 1. For each bottle, the participant will follow their randomly assigned (Group 1 or Group 2 randomization) preparation instructions to measure the required amount of powdered formula. The participant will dispense the respective number of scoops of powdered formula into the formula bottle depending on which size bottle is being prepared. After all powdered formula is dispensed into the feeding bottle, PBRC staff will weigh the formula bottle with powdered formula only. The participant will continue following the instructions and pour water into the bottle and mix the formula. PBRC staff will weigh the formula bottle. This procedure will be repeated to assess intra- individual variability. Bottles will be weighed (to the nearest tenth of a gram) using a METTLER TOLEDO PB3001 scale, and dry formula and prepared formula weights will be recorded. Study staff who record the formula weights will be blinded to the randomization assignment and intended bottle size.

5. PARTICIPANT SAFETY AND CONFIDENTIALITY

5.1. Risks to participants

This study involves humans, but does not meet the definition of a clinical trial because there is no prospective intervention that may impact health. This study does not involve major risk to screeners and trial participants. Efforts to minimize the potential risks of the assessment methods and outcome variables include monitoring by the investigators to assure there are no incidents that occur while at Pennington Biomedical Research Center as a result of participating in the research.

Potential Risks associated with the study procedures include (presented in alphabetical order):

- Body weight. There is no risk to participants who record their body weight.
- Focus groups. There is minimal risk associated with participation in a focus group. Participants will be told that the discussion during a group is confidential prior to the start of a discussion. Participants will be encouraged to participate in the discussion, but will not be required to do so if they feel uncomfortable.
- Infant formula preparation. There is no risk to participants who prepare infant formula. The formula will be poured out after preparation, and no formula will be consumed.

- Interview: There is no known or anticipated risk associated with the completion of an interview. Participants will be encouraged to answer all questions, but will be told that they can choose not to answer any questions if they feel uncomfortable answering them. Responses to the questions will be coded to protect confidentiality.

5.2. Adverse events

Pennington Biomedical Research Center is an AAHRPP accredited institution and, above all else, is committed to ensuring and maintaining the safety of its participants. Participants in the study will come to Pennington Biomedical Research for one visit and will not be followed longitudinally. Therefore, adverse events and medications will not be tracked. There are three physicians on site at Pennington Biomedical Research Center who will be available if an incident occurs during a study visit. Study staff will follow institutional procedures for reporting any incident.

Protection of subjects from risks related to the study is of paramount concern to investigators. Due diligence will be applied to ensure that study subjects are not exposed to undue or untoward risk. Remedial action, including additions and changes to the protocol, will be taken as appropriate. The specific reporting mechanism currently in place is also outlined in PBRC HRPP Policy 8.0 Unanticipated Problems Involving Risks to Subjects or Others. While Federal guidelines require that Unanticipated Problems Involving Risks to Subjects or Others [21 CFR 56.108(b)] be reported to the IRB [45 CFR 46.103(b)(5)], related internal and external events involving risk but not meeting the prompt reporting requirements should be reported to the IRB in summary form at the time of continuing review. Surveillance and reporting procedures are summarized in the following section.

5.2.1. Surveillance

All incidents will be recorded and reviewed by the study Principal Investigator and a Center physician. Proper action as directed by Center standard operating procedures or physician advice will be followed.

5.2.2. Reporting

The following events may represent unanticipated problems involving risks to subjects or others and should be promptly reported to the IRB:

Breach of confidentiality involving risks

- Event requiring prompt reporting (Report only when required by the protocol, sponsor, or funding agency.)
- New information (Report information indicating an unexpected change in risks or potential benefits, e.g., literature/scientific report or other published finding.)
- Subject complaint (complaints indicating unanticipated risks or those that cannot be resolved by the research staff.)
- Unapproved change made to the research to eliminate an apparent immediate hazard
- Other problem or finding (e.g., loss of study data, a subject becomes a prisoner while participating in research)
- New information that may affect adversely the safety of the participants or the conduct of the clinical trial.
- Any changes significantly affecting the conduct of the clinical trial or increasing the risk to participants.

Both internal events and external events that may represent unanticipated problems involving risks to subjects or others should be promptly reported. Unanticipated problems involving risks to subjects or others will be reported within 10 working days of the Principal Investigator or research staff becoming aware of the

unanticipated problem. Events resulting in temporary or permanent interruption of study activities by the investigator or sponsor to avoid potential harm to subjects should be reported within 48 hours when possible.

5.3. Stopping rules

There is minimal risk for participating in this trial. The most likely scenario that would indicate a cessation of the study would be failure to recruit participants. Nevertheless, in addition to monitoring recruitment, we also will monitor the rates of injury in our participants. The study investigators will alert the IRB, if a larger than reasonably expected injury rate occurs in our participants. Other issues that are related to the stopping rules include:

- New information – It is unlikely that new information will become available during this study that would result in discontinuing the trial.
- Limits of assumption – It is possible that the value of data analysis will be limited by differences between the intervention groups at baseline or because of study dropouts or missing data. Baseline differences will be analyzed annually and effects on the power to detect differences in the outcome measures will be evaluated and discussed with the PI and other officials. Although an excessive number of dropouts could occur, this has not been our past experience. In CALERIE study (24 weeks), the dropout rate was only 2% (1 out of 36 enrolled). If the dropout rate for the proposed study exceeds 15%, the study coordinator will initiate a meeting with the PI to discuss strategies to increase retention. If the dropout rate exceeds 25%, the safety officer will meet with the study investigators to determine whether or not the study should continue.
- Limit of rules – We acknowledge that circumstances, other than what are listed, may justify stopping the study.

5.4. Confidentiality

All volunteers are assured of their anonymity and confidentiality both verbally and in the informed consent form. The clinical facilities are strictly limited to the staff of the research institution and to research volunteers. This is accomplished by a variety of stringent security measures. All medical records are stored in locked areas. Access to these areas is limited to the clinical support staff, director of the clinical facilities, and the PIs. Volunteers' medical records are filed according to ID numbers. All forms on the chart, with the exception of consent form, display only the ID number. Electronic data storage is similarly restricted with only the PIs and authorized persons having access to databases containing confidential clinical records, i.e. those containing name, Social Security Number or other identifying information.

Data will be collected from participants. Data are confidentially collected from study participants and are only used for research purposes. All records are kept in locked file cabinets, and participant data can be identified only by number. Data are used only in aggregate, and no identifying characteristics of individuals are published or presented.

6. DATA MANAGEMENT

6.1. Sample Size Consideration

In the Baby Bottle study, participants were asked to prepare a randomly ordered set of liquid baby formula (2, 4, 6, or 8 fl oz). Estimated proportions of participants over-scooping dry formula for bottles containing each amount were obtained from this preliminary data. A separate power analysis for the proposed study was carried out for each formula amount with the Baby Bottle estimates used to represent expected proportion of participants over-scooping dry formula when using the manufacturer preparation instructions. To ensure a well powered study, each estimate from the Baby Bottle data was reduced by an additional 15%. The most conservative results from the power analyses are presented in **Table 4** and provide a sufficient sample size to

achieve desired power when comparing the control and experimental group proportions of over-scooping for any individual formula amount as well as across all amounts. In the proposed study, we hope to see the proportion of participants over-scooping formula reduced to 50% following use of the new preparation instructions. 75 participants will be enrolled in each study group, ensuring 80% power to detect this decrease.

Table 4. Sample size calculations¹

Power (%)	Proportion over-scooped: OLD	Proportion over-scooped: NEW	N Per Group
80	0.8	0.7	294
80	0.8	0.6	82
80	0.8	0.5	39
80	0.8	0.4	23

¹*Old Proportion* represents the proportion of participants expected to over-scoop formula when using the existing instructions. *New Proportion* represents the reduced proportion of participants that are expected to over-scoop formula when using the new instructions.

